6.3 Geometric Measurements

- Inter-implant distance (distal implants).
- Cantilever length (distal extension).
Measurements obtained from final CAD designs.

6.4 Clinical Outcomes

- Implant survival
- Prosthetic survival
- Mechanical complications (e.g., chipping, screw loosening, framework fracture)
- Biological complications

6.5 Patient-Reported Outcomes

- OHIP-14
- VAS satisfaction (0–10)

7. Outcome Measures

Primary Outcome

Marginal Bone Loss (mm)

Change in peri-implant marginal bone level measured from baseline to 12 months.
Higher values = greater bone loss (worse outcome).

Secondary Outcomes

1. Implant and Prosthetic Survival Rate

Percentage surviving without removal or failure. Higher % = better outcome.

2. Patient-Reported Outcomes

- OHIP-14 (0–56; higher = worse)
- VAS satisfaction (0–10; higher = better)

3. Mechanical and Biological Complications

Presence/absence and type of event.

8. Statistical Analysis Plan

- Normality: Shapiro–Wilk test
- Between-group comparisons: Two-way ANOVA
- Morphology subgroups: One-way ANOVA with Bonferroni
- Paired comparisons (bimaxillary patients): Paired t-test
- Correlations: Pearson (separately for each arch)
- Significance level: $\alpha = 0.05$

Secondary analyses are exploratory.

9. Ethical Considerations

- Approved by UIC Ethics Committee (REST-ECL-2020-02).
- Conducted in accordance with the Declaration of Helsinki.
- All participants provided informed consent.
- Data stored securely and pseudo-anonymized.

10. Data Management

- Coded, de-identified datasets stored on secure servers.
- Access limited to authorized researchers.
- Data retained for 15 years.

11. Study Timeline

- Start Date: December 2024

- Primary Completion Date: December 2025
- Study Completion Date: December 2025

12. Dissemination Plan

Results will be submitted for peer-reviewed publication and presented at scientific conferences. No identifying participant information will be released.

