Twelve-Month Short-Term Marginal Bone Remodeling at Monolithic Zirconia Full-Arch Prostheses in the Maxilla and Mandible: A Clinical Study

NCT Number:
NCT: *Not yet assigned*

Document Type:
Study Protocol

Document Date: July 9, 2020

Version:
1.0

Sponsor:
Universitat Internacional de Catalunya (UIC)

Principal Investigator: [name]

Study Sites:
Universitat Internacional de Catalunya

STUDY PROTOCOL

1. Background and Rationale

Monolithic zirconia full-arch implant-supported prostheses have gained widespread clinical use due to their high mechanical strength, esthetic longevity, and lower chipping risk compared to veneered restorations. Despite increasing adoption, limited evidence exists regarding whether marginal bone remodeling differs between maxillary and mandibular zirconia rehabilitations and whether mandibular morphology or arch geometry influence early remodeling outcomes.

Mandibular deformation during function (“mandibular flexure”) and anatomical variations such as U-shaped vs V-shaped mandibular arches may contribute to differences in bone response. This study evaluates early remodeling patterns under strictly standardized surgical and prosthetic conditions to determine whether mandibular anatomy plays a measurable role.

2. Study Objectives

Primary Objective

To compare 12-month marginal bone remodeling (MBL) between maxillary and mandibular full-arch monolithic zirconia implant-supported prostheses.

Secondary Objectives

- To evaluate whether mandibular morphology (U-shaped vs V-shaped) affects early marginal bone remodeling.
- To assess associations between arch geometry (inter-implant distance, cantilever length) and MBL.
- To evaluate 12-month implant and prosthetic survival rates.
- To assess patient-reported outcomes (OHIP-14 and VAS satisfaction).
- To document biological and mechanical complications.

3. Study Design

This is a prospective observational cohort study with a 12-month follow-up period.

All patients receive standard-of-care implant placement and monolithic zirconia full-arch prosthetic rehabilitation. No experimental intervention is assigned.

Study Groups

- **Group 1:** Maxillary full-arch rehabilitations
- **Group 2:** Mandibular full-arch rehabilitations
 - Sub-analysis: U-shaped vs V-shaped mandibles

Observation Period

Baseline (prosthesis delivery) → 12 months.

Sample Size

49 rehabilitated arches in 40 edentulous patients.

Power >85% to detect a 0.2 mm difference in MBL (SD 0.30 mm).

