4. Study Population

Inclusion Criteria

- Age \geq 50 years
- Edentulous maxilla and/or mandible
- Adequate bone volume for 6–8 implant placement
- Non-smokers or light smokers (<10 cigarettes/day)
- Able to provide informed consent

Exclusion Criteria

- Bruxism
- Bisphosphonate therapy
- Uncontrolled systemic diseases
- Contraindications to implant surgery
- Active oral infection or poor hygiene

5. Surgical and Prosthetic Procedures

- Guided placement of 6–8 NobelParallel TiUltra implants per arch.
- Immediate loading with a PMMA provisional prosthesis within 48 hours.
- Delivery of the definitive monolithic zirconia prosthesis at 3 months using a full digital workflow.
- Standardized radiographs and follow-up examinations.

6. Assessments

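### The main maxilla–mandible test is a two-way ANOVA with no stated patient or arch term, although 9 of 40 patients sit in both groups and each arch carries six to eight implants

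*Protocol*

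**What the plan says.** - **Objective** (Protocol, Section 2): "To compare 12-month marginal bone remodeling (MBL) between maxillary and mandibular full-arch monolithic zirconia implant-supported prostheses".
- **Sample** (Section 3, Sample Size): "49 rehabilitated arches in 40 edentulous patients". Section 4 admits patients with "Edentulous maxilla and/or mandible", so one patient can supply both jaws.
- **Implants** (Section 5): "Guided placement of 6–8 NobelParallel TiUltra implants per arch".
- **Primary outcome** (Section 7): "Change in peri-implant marginal bone level measured from baseline to 12 months". Averaging over the implants of an arch is not mentioned.
- **Main test** (Section 8): "Between-group comparisons: Two-way ANOVA". Neither factor is named, nor is the unit of analysis, and no patient or arch effect is specified.
- **Only recognition of the overlap** (Section 8): "Paired comparisons (bimaxillary patients): Paired t-test". How this test relates to the primary comparison is not stated.

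**The concern.** An ordinary ANOVA assumes independent observations. Two features of this design break that assumption, and they pull in opposite directions.

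- **Same patient in both groups.** Positive correlation between a patient's two jaws makes the jaw difference more precise than the ANOVA believes. The interval is too wide and power is lost.
- **Several implants in one arch.** Implants in the same arch share surgeon, prosthesis and host. Treated as independent, they make the jaw difference look far more precise than it is.

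The unstated unit therefore decides whether the primary p-value is mildly conservative or several times too liberal, and that choice could be made after the data are seen.

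**Working it through.** **Inputs.** From the Protocol: 49 arches, 40 patients, six to eight implants per arch, a difference of 0.2 mm, SD 0.30 mm, α = 0.05 (taken as two-sided). Assumed, because the Protocol gives neither: a 25:24 jaw split, and a range of correlations.

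**Overlap.** A patient has at most two arches, so 49 − 40 = 9 patients have both and 31 have one. Implants number 49 × 6 = 294 to 49 × 8 = 392.

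**The plan's own power figure (above 85%).** With 49 independent arches, SE = 0.30 × √(1/25 + 1/24) = 0.0857 and 0.2/0.0857 = 2.333. Power = Φ(2.333 − 1.960) = 64.5% (62.7% by noncentral t). With 40 patients split 20:20 it is 55.9%. With 294–392 implants taken as independent it exceeds 99.9%. The stated figure is thus met only at implant level. That is a separate sample-size matter, but it keeps the implant reading open.

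**Reading 1: arch means.** The true SE is √[0.09 × (1/25 + 1/24 − 2ρ × 9/600)]. The ratio of ANOVA SE to true SE is 1/√(1 − 18ρ/49), which does not depend on the jaw split. Type I error and power are simulated (20,000 runs).

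| ρ (within patient) | True SE | ANOVA SE too wide by | ANOVA type I error | ANOVA power | Kenward-Roger mixed model: type I error | power |
|---|---|---|---|---|---|---|
| 0.1 | 0.0841 | 2% | 4.4% | 63% | 5.3% | 63% |
| 0.3 | 0.0809 | 6% | 4.0% | 63% | 5.7% | 66% |
| 0.5 | 0.0775 | 11% | 3.1% | 64% | 5.3% | 72% |

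With a 30:19 split, power at ρ = 0.5 is 61.8% for the ANOVA and 70.6% for the mixed model.

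**Reading 2: implants.** With m implants per arch, total ICC = patient part + arch part, and the overlap taken into account, the ANOVA understates the variance of the jaw difference by the factor

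F = 1 + (m − 1) × ICC − m × (patient part) × 18/49,

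and the approximate type I error is 2 × [1 − Φ(1.96/√F)].

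| Total ICC (patient + arch) | F, m = 6 / 8 | Formula | Simulated (10,000 runs) |
|---|---|---|---|
| 0.10 (0.05 + 0.05) | 1.39 / 1.55 | 9.6% / 11.6% | 9.8% / 11.9% |
| 0.30 (0.2 + 0.1) | 2.06 / 2.51 | 17.2% / 21.6% | 17.4% / 21.7% |
| 0.50 (0.3 + 0.2) | 2.84 / 3.62 | 24.5% / 30.3% | 25.0% / 30.3% |

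An independent simulation that split the ICC equally between patient and arch gave 9–12%, 18–23% and 26–32%.

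**Reading 3: patient is the unnamed second factor.** The jaw contrast is then purely within patient. Residual df = 49 − 40 − 1 = 8, and the 31 single arches add nothing to it. This is equivalent to a paired t-test on 9 pairs. The SD of a difference is 0.30 × √(2(1 − ρ)) and the noncentrality is 0.2 × √9 divided by that SD: 1.49, 1.69 and 2.00 at ρ = 0.1, 0.3 and 0.5. Power is 26%, 32% and 42%. The separate paired t-test in Section 8 has the same power and leaves the ANOVA as it is.

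**The case against.** The strongest reply is that the factors are unnamed, so the text does not rule out a patient term, and that a separate SAP may supply the detail. The text also leans towards the arch as unit: the sample size and groups are in arches, morphology and geometry are arch-level measures, and a paired t-test needs one value per jaw. On that reading the error is small and on the safe side. The mixed model then replaces a conservative test with one at 5.3–5.7% and gains little at low correlation. The large type I figures need both the less likely unit and ICCs that the Protocol does not give.

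Much of this stands. The arch is the likelier unit, the damage there is modest, and the overlap was noticed, since the paired test is listed. It does not clear the plan. Section 8 fixes a method rather than deferring it. Naming patient as the second factor throws away 31 of the 49 arches for the jaw contrast. The implant reading is not excluded by the outcome definition, and it is the only one under which the stated power is met.

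**Conclusion.** The concern holds. None of the three readings gives a sound primary test that uses all the data: arch means give an SE 2–11% too wide, implants give about two to six times the nominal false-positive rate, and patient as a factor leaves 9 pairs with 8 df. The overlap of 9 patients follows directly from the Protocol. The sizes rest on assumed correlations (0.1–0.5 within patient; 0.10–0.50 total ICC for implants) and, for the simulated power and type I error, on an assumed jaw split. The power figures here serve only to compare methods. This should be fixed before analysis. It is not grave if the arch is confirmed as the unit.

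**What to change.** In Section 8:

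1. State the unit of analysis (arch mean or implant).
2. Make one linear mixed model for 12-month MBL change the single primary test: jaw as fixed effect, a random intercept for patient and, if implant-level data are used, a random intercept for arch within patient.
3. Fit by REML with Kenward-Roger standard errors and degrees of freedom, and keep the patient term even if its variance is estimated as zero. Without the small-sample correction the simulated type I error on arch means was 7–8%.
4. Report the jaw difference with a 95% confidence interval, and keep the paired t-test as a sensitivity analysis.

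The cost is wording and standard software, with no new data. There are limits. The within-patient correlation is estimated from 9 pairs, and in simulation it came out as zero in 39%, 20% and 7% of runs at true values of 0.1, 0.3 and 0.5. The power gain over the ANOVA on arch means is therefore only about 0, 3 and 8 points, and a slight type I excess (up to 5.7%) remains.

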6.2 Mandibular Morphology Classification

- CBCT-based classification using validated criteria (intercanine/intermolar ratio and anterior arch angle).
- U-shaped vs V-shaped categorization.

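### Section 8 names a two-way ANOVA for a primary comparison that has one two-level factor, and no second factor is given

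*Protocol*

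**What the plan says.** The primary objective (protocol, Section 2) is "To compare 12-month marginal bone remodeling (MBL) between maxillary and mandibular full-arch monolithic zirconia implant-supported prostheses". Section 3 defines two groups, "Maxillary full-arch rehabilitations" and "Mandibular full-arch rehabilitations", and places one item under the second: "Sub-analysis: U-shaped vs V-shaped mandibles". Section 6.2 classifies the shape of mandibles only. Section 7 defines the primary outcome as "Change in peri-implant marginal bone level measured from baseline to 12 months".

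Section 8 then assigns the test: "Between-group comparisons: Two-way ANOVA". It names no factors and no interaction. Separate lines give morphology a one-way ANOVA with a Bonferroni adjustment, bimaxillary patients a paired t-test, and arch geometry Pearson correlations within each arch. Section 3 counts 49 arches in 40 patients.

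**The concern.** A two-way ANOVA needs two factors. The primary objective supplies one, jaw. Time is not an evident second factor, because the outcome is already the difference between the two time points. An analyst who follows Section 8 must therefore supply the second factor.

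The choice matters because the candidates do not answer the same question. Some leave maxilla minus mandible intact, one can make the jaw coefficient undefined, and one restricts the comparison to a small subset of patients. The primary test could thus be settled after the data are seen, and two analysts could reach different primary conclusions from the same plan.

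**Working it through.** **Inputs.** From the protocol: 49 arches and 40 patients, a difference of 0.2 mm and an SD of 0.30 mm (Section 3), and alpha 0.05 (Section 8). Assumed, because not given: one value per arch, a two-sided test, 24 maxillae and 25 mandibles, 13 U and 12 V among the mandibles, and within-patient correlations from 0 to 0.7. The rank results need only that each group is non-empty.

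**The plan's own figure.** Section 3 states power above 85% but ties it to no model. A plain two-group comparison gives SE = 0.30 × √(1/24 + 1/25) = 0.0857 mm and power Φ(0.2/0.0857 − 1.96) = 64.5%. The stated figure is not reproduced this way. That is a separate matter, and nothing below rests on it. It does mean that the power statement cannot be used to work out which second factor was intended.

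**Shape as an additive or crossed factor.** Code jaw as 1 for mandible, with indicators for U and V and maxilla as the level without a shape. Every mandible is U or V and no maxilla is either, so

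jaw = U + V.

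The columns intercept, jaw, U and V have rank 3, not 4. The jaw coefficient is not estimable. The combination jaw + ½U + ½V, which is the mandibular average minus the maxilla, is estimable, but a standard two-way table does not report it as the jaw effect.

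**Shape left blank for maxillae.** Complete-case fitting drops all 24 maxillae. Among the 25 mandibles jaw is constant and equals the intercept: three columns (intercept, jaw, V), rank 2. No jaw comparison remains.

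**Shape nested within mandible, or three groups with a contrast.** Three columns, rank 3. Maxilla minus the equally weighted mean of U and V has

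SE = 0.30 × √(1/24 + ¼(1/13 + 1/12)) = 0.0858 mm,

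against 0.0857 mm for the plain comparison. The jaw contrast is fully recovered. The cost is this small because the assumed U/V split is nearly even.

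**Patient as a fixed second factor.** If each patient contributes at most two arches, 49 − 40 = 9 patients have both and 40 − 9 = 31 have one. Jaw plus 40 patient columns gives 41 columns of rank 41, so jaw is estimable. However, each of the 31 single arches is absorbed by its own patient term. The residual has 49 − 41 = 8 degrees of freedom, and the jaw test is the paired t-test on nine pairs that Section 8 already lists. The SE is 0.30 × √(2(1 − ρ))/√9. For comparison, a patient random effect uses all 49 arches (nine pairs, 15 single maxillae, 16 single mandibles):

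| Assumed ρ | SE, patient fixed (mm) | SE, patient random (mm) | Ratio |
|---|---|---|---|
| 0 | 0.1414 | 0.0857 | 1.65 |
| 0.3 | 0.1183 | 0.0797 | 1.48 |
| 0.5 | 0.1000 | 0.0733 | 1.36 |
| 0.7 | 0.0775 | 0.0629 | 1.23 |

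Power for 0.2 mm with patient fixed (noncentral t, 8 df) runs from 24% at ρ = 0 to 62% at ρ = 0.7.

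**Bimaxillary status as the second factor.** Jaw, status and their product give four columns of rank 4, so jaw is estimable. The protocol does not propose this factor.

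**The case against.** The strongest reply is that Section 8 never makes shape the second factor. It gives morphology a test of its own, and Section 3 calls it a sub-analysis; both point away from shape in the primary model. Other variables in the protocol could cross with jaw without aliasing: smoking category (Section 4), implant number (Section 5) and bimaxillary status. Naming factors is also often left to a separate analysis plan.

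Much of this stands. A reader might infer that the jaw effect is not estimable in the planned primary analysis, or that no admissible reading yields the primary contrast. The documents support neither inference. Aliasing follows only from additive or crossed coding of shape, nested coding removes it, and other second factors leave jaw estimable. A reader might also infer a jaw-by-time analysis that ignores pairing and loses power. Nothing in the protocol prescribes one, and Section 7 defines the outcome as a change.

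The point about a later analysis plan carries less weight. Section 8 does not leave the method open. It fixes a two-factor method for a one-factor question, and the protocol designates none of the possible second factors for that role.

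**Conclusion.** The point holds as a mismatch between the stated primary test and the design, not as proof that the primary analysis cannot be done. The protocol's groups form one two-level factor. The only other arch grouping it defines cannot be crossed with jaw (rank 3 of 4, or loss of every maxilla if shape is blank), though nested or three-group coding keeps the contrast at almost the same SE. A fixed patient factor would rest the contrast on nine patients, with an SE 1.23 to 1.65 times that of a random patient effect over the assumed correlations.

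The aliasing is algebraic and does not depend on the assumed split. The count of nine assumes at most two arches per patient. The SEs and power depend on the assumed splits and correlations, and on reading the 0.30 mm as the SD of one arch's change.

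**What to change.** In Section 8, replace the two-way ANOVA with wording such as:

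*Primary analysis: one planned contrast, maxilla minus mandible (all mandibles together), on the 12-month change in marginal bone level, with a 95% confidence interval, from a model in which jaw is the only group factor and which accounts for patients contributing two arches (for example, a patient random effect). Morphology: U minus V is estimated among mandibles only and is never entered as a factor crossed with jaw.*

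The paired t-test in bimaxillary patients can stay as a supporting analysis. If the investigators did intend a particular second factor, they should name it, say how it is coded, and state which contrast is primary. The cost is one or two sentences and no new data.

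### Correlating geometry with bone loss only within each jaw splits 49 arches into two small analyses and gives no estimate of whether the relation differs by jaw

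*Protocol*

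**What the plan says.** Protocol Section 8 gives one line on geometry: "Correlations: Pearson (separately for each arch"). I read arch here as jaw, since the study groups in Section 3 are maxillary and mandibular rehabilitations. No other listed method links geometry to MBL: the two-way ANOVA names no factors and no geometry term, the one-way ANOVA concerns mandibular shape, and the paired t-test concerns bimaxillary patients.

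The objective served is secondary (Section 2): "To assess associations between arch geometry (inter-implant distance, cantilever length) and MBL". It names no difference between jaws. The rationale in Section 1 is more pointed. It starts from mandibular flexure, asks "whether mandibular morphology or arch geometry influence early remodeling outcomes", and sets out "to determine whether mandibular anatomy plays a measurable role".

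The sample is "49 rehabilitated arches in 40 edentulous patients" (Section 3). Section 8 sets the significance level at 0.05 and adds: "Secondary analyses are exploratory".

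**The concern.** Reporting geometry separately by jaw puts two results side by side. In a study motivated by mandibular flexure, a reader who sees a significant correlation in the mandible and none in the maxilla will be drawn to a mandible-specific explanation. Significance in one group and not in the other is not evidence that the groups differ, and the plan supplies nothing that would estimate the difference.

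There are two further costs. Each correlation uses about half the arches, so even the plain association that the objective asks for is estimated less precisely than the data allow. And Pearson's r depends on how widely inter-implant distance or cantilever length varies within a jaw, so two r values can differ when the slope in mm of bone per mm of geometry is the same.

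**Working it through.** **Inputs.** From the protocol: 49 arches, 40 patients, significance level 0.05. With at most two arches per patient, 49 − 40 = 9 patients contribute both jaws. Assumed, because the protocol does not say: 24 maxillary and 25 mandibular arches (also 29/20 and 20/29), one MBL value per arch, two-sided tests, independence between jaws.

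**The plan's own figure.** None is given for the correlations. The sample-size statement, "Power >85% to detect a 0.2 mm difference in MBL (SD 0.30 mm", concerns a difference in means. For 24 versus 25 arches it gives 0.2 / (0.30 × √(1/24 + 1/25)) = 2.33, and Φ(2.33 − 1.96) = 64.5%, not above 85%. That is a separate matter and is not used below.

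**Correlation needed for p < 0.05.** r = t / √(n − 2 + t²). For n = 24: 2.074 / √(22 + 4.30) = 0.40. For n = 25: 2.069 / √(23 + 4.28) = 0.40. For n = 20 it is 0.44, and for n = 29 it is 0.37.

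**Chance discordance when the jaws are identical.** Let p1 and p2 be the simulated power in maxilla and mandible at the same true r (200,000 replicates per jaw). Exactly one significant: p1(1 − p2) + p2(1 − p1). Mandible only: p2(1 − p1).

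| Common true r | p1 (n = 24) | p2 (n = 25) | Exactly one jaw | Mandible only |
|---|---|---|---|---|
| 0 | 5.0% | 5.0% | 9.5% | 4.8% |
| 0.2 | 15.4% | 16.0% | 26.5% | 13.6% |
| 0.3 | 30.0% | 31.4% | 42.5% | 22.0% |
| 0.4 | 50.6% | 52.7% | 50.0% | 26.0% |
| 0.5 | 72.9% | 75.0% | 38.5% | 20.3% |
| 0.6 | 90.1% | 91.4% | 16.9% | 9.1% |

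For example, at r = 0.4: 0.506 × 0.473 + 0.527 × 0.494 = 0.50, of which mandible only is 0.527 × 0.494 = 0.26.

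The split matters more for the mandible-only figure than for the total. For r = 0.3 to 0.5, exactly one jaw is significant in 41–51% under either uneven split. Mandible only is 27–34% with 29 mandibles and 20 maxillae, and 12–18% with 20 mandibles and 29 maxillae.

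**A direct comparison.** Fisher's z serves as a proxy for the interaction test: SE = √(1/21 + 1/22) = 0.305. In the same simulations its false-positive rate was 5% at every common r. Its power is low:
- r = 0 versus 0.3: Φ(0.310/0.305 − 1.96) = 17%.
- r = 0 versus 0.5: Φ(0.549/0.305 − 1.96) = 44%.
- For 80% power the z difference must be 2.80 × 0.305 = 0.855, which is r = 0.69 against 0.

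**Precision of the association itself.** At a common r = 0.4, atanh(0.4) = 0.424. One jaw of 25: Φ(0.424 × √22 − 1.96) = 51%. All 49 arches adjusted for jaw: Φ(0.424 × √45 − 1.96) = 81%. Simulation agrees closely (about 52% and 82%).

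**Dependence of r on spread (illustration only).** Take r = 0.50 with predictor SD 1, slope 0.5 and residual variance 0.75. Halve the predictor SD in one jaw and keep slope and residual variance: r = 0.25 / √(0.0625 + 0.75) = 0.28. Power at n = 24 falls from 73% to 26% with no change in the slope. The protocol gives no spreads, so this shows the mechanism and predicts nothing.

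**The case against.** The best defence is that the plan does what its objective asks. The objective is to assess associations; correlations within each jaw do that. No passage says that the two coefficients will be contrasted or that discordant p-values will be read as a jaw effect, and secondary analyses are declared exploratory. All of this stands. A reader might infer that the study's geometry question is effect modification by jaw and that the plan itself commits the significant-here, not-there error. The text does not support that: flexure is given as motivation, and the misreading would occur in a later report.

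Stratifying also has merits. Within one jaw each patient contributes at most one arch, so an arch-level correlation avoids the clustering from the 9 bimaxillary patients. It also keeps a jaw difference in mean MBL from creating a spurious pooled association. Both merits are real, but a model with a jaw term and errors clustered by patient retains them.

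Low interaction power is also a fair point. It argues for reporting the difference with its interval. It does not make two unconnected p-values informative about that difference. A separate SAP could add an interaction model, but Section 8 already fixes the method as per-jaw Pearson correlation, so this is a stated choice and not merely an omitted detail.

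**Conclusion.** The point holds as a limited one. Section 8 fixes a method that uses the data inefficiently and leaves the mandible-specific reading of geometry without an estimate. The primary outcome is untouched, and the stated secondary objective is answered, though less precisely than it could be.

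The relevant size is the mandible-only pattern, about 20–26% for a common true r of 0.3 to 0.5. A reader might instead take the 39–50% discordance as the risk of a spurious mandibular finding. That overstates it about twofold, because maxilla-only significance would not support flexure. Even 20–26% covers the range of r where the risk is highest; it is 14% at r = 0.2, 9% at 0.6 and 5% at 0.

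These figures rest on the assumed 24/25 split, one value per arch, independence between jaws and a two-sided 0.05 level. They apply to one geometric measure; the protocol names two, which makes four correlations.

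**What to change.** Replace the correlation line in Section 8 with one exploratory regression of arch-level MBL on jaw and geometry for each geometric measure, using cluster-robust errors by patient or a patient term for the bimaxillary patients. Report first the jaw-adjusted common slope in mm of MBL per mm of geometry. Then add the jaw × geometry term and report the slope in each jaw and their difference with a 95% CI. State that no jaw-specific geometry effect will be claimed from discordant per-jaw p-values. The per-jaw Pearson coefficients can stay as description.

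The cost is two or three sentences in Section 8 and no new data. The downside is that the interval for the difference will probably be wide, so the likely result is that the study cannot tell whether the jaws differ in this respect. With only 9 pairs, a patient variance component would be poorly estimated, which favours the cluster-robust version.
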